### 5.6.8.1 Diurnal Involuntary Sleep Attacks

The number and total duration of diurnal involuntary sleep attacks will be recorded in the subject diaries. These data will be summarised as numeric variables as described in section 5.6.8.

The following tables will be presented:

Table 15.3.14.1.S Summary of Diurnal Involuntary Sleep Attacks – Full Analysis

Table 15.3.14.2.T Summary of Diurnal Involuntary Sleep Attacks – Full Analysis

The number and duration of diurnal involuntary sleep attacks will be summarised using default summary statistics for each trial period. The change from baseline will be displayed for each post-baseline period.

### 5.6.8.2 Somnolence Episodes

The number of somnolence episodes each day will be collected in the subject diaries. It will be summarised as a numeric variable as described in section 5.6.8.

The following tables will be presented:

Table 15.3.15.1.S Summary of Somnolence Episodes – Full Analysis

Table 15.3.15.2.T Summary of Somnolence Episodes – Full Analysis

The number of somnolence episodes will be summarised using default summary statistics for each trial period. The change from baseline will be displayed for each post-baseline period.

### 5.6.8.3 Other Efficacy-Related Variables

Other efficacy-related variables collected in the subject diaries include:

- Get-up time
- Total time (hours) slept last night
- Wake-up periods during night sleep:
  - Number (<5, between 5 and 10, >10)
  - Total duration (minutes)
- Voluntary naps:
  - Number
  - Total duration (minutes)
- Number of caffeinated drinks
- Going-to-bed time

**Time in bed** will be calculated as the difference in hours between the get-up time and the going-to-bed time of the preceding day. Time in bed will not be calculated if either of the datetime values are completely or partially missing.

**Adjusted total time slept** in hours will be calculated as follows:

$$Adj. \text{ total time slept} = \min(\text{total time slept}, \text{time in bed} - \text{wake} - \text{up period duration})$$

With the exception of the number of wake-up periods during night sleep, these data will be summarised as numeric variables as described in section 5.6.8.

The following tables will be presented:

Table 15.3.16.1.S Summary of Other Efficacy-Related Diary Data – Full Analysis

Table 15.3.16.2.T Summary of Other Efficacy-Related Diary Data – Full Analysis

The secondary diary data will be summarised for each trial period using default summary statistics or frequency tabulations, as appropriate.

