## 5.6.8 Subject Diary Data

Over the course of the trial, subjects will fill out paper-based diaries concerning their daily sleep and IMP intake patterns. One screening diary and three treatment diaries will be issued at visit VS1, and visits VR, V1C, and V2C respectively, and collected at visits VR, V1C, V2C, and V3B/EDV. The diaries will be filled in continuously from visit VS1 to V3B/EDV, including the washout periods after treatment periods I and II.

Analysis of drug exposure data collected from subject diaries is discussed in section 5.4.1.

Efficacy-related data collected from patient diaries will be summarized over the respective trial period (baseline, washout 1, washout 2, and treatment 1, 2, or 3) for the purpose of displaying them in summaries. Numeric variables will be standardized to amount per day, and for categorical variables subjects will be included in every category that occurred to them in the given period.

If there are less than 3 non-missing values over the course of a treatment or washout period for a given variable, it will be set to missing for the respective period in summaries. For treatment periods, only the last 3 non-missing values per parameter will be aggregated in summaries order to capture the full effect of the IMP.

All diary data will be listed.

Listing 16.2.9.5 Diary Sleep Data – Enrolled

Listing 16.2.9.6 Diary Exposure Data – Enrolled

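### SAP 5.6.8.3: taken literally, the adjusted-sleep formula subtracts minutes from hours, and no rule is given for summarising or dating bedtimes around midnight

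*SAP*

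**What the plan says.** SAP 5.6.8.3 covers diary variables that are not among the listed endpoints. Night sleep is collected in hours ("Total time (hours) slept last night"). Time awake during the night is collected as a total in minutes (its list entry begins "Total duration (minutes").

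Two variables are derived:

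- **Time in bed.** "Time in bed will be calculated as the difference in hours between the get-up time and the going-to-bed time of the preceding day". The inputs are dates with clock times: "Time in bed will not be calculated if either of the datetime values are completely or partially missing".
- **Adjusted total time slept.** "Adjusted total time slept in hours will be calculated as follows". The expression that follows takes the smaller of total time slept and time in bed less wake-up period duration. It contains no factor of 60 and no provision for a negative result.

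Only the count of night awakenings, which is recorded in bands, is exempt from numeric treatment. For everything else in the list, including going-to-bed time and get-up time, the section says that "these data will be summarised as numeric variables as described in section 5.6.8". Section 5.6.8 then says "Numeric variables will be standardized to amount per day" and, for treatment periods, uses the three latest available values. Neither section gives a reference point for a clock time.

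The results go to Tables 15.3.16.1.S (by sequence) and 15.3.16.2.T (by treatment), on the Full Analysis Set, as descriptive summaries.

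**The concern.** Three rules in one short section either cannot be applied as printed or leave a gap. The sleep formula mixes units. A bedtime has no meaningful amount per day, and its plain average fails when values fall on both sides of midnight. The time-in-bed rule does not cover a subject who goes to bed after midnight.

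The variables are of some interest. Protocol Table 1 lists insomnia among the adverse events of both components, and protocol 1.4.2 hopes for better night sleep. Under plain averaging, a treatment that pushed some bedtimes past midnight would appear to move the mean bedtime earlier, which is the wrong direction. The unit error can also be hard to see: with only a few minutes awake, the literal formula returns a low but believable number of hours.

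**Working it through.** The plan states no figure on this point, so there is nothing to reproduce. The units and rules below come from SAP 5.6.8 and 5.6.8.3. The diary values are illustrative assumptions.

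**1. Adjusted total time slept.** Assume time in bed 8 h and reported sleep 6.5 h, with w minutes awake.

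- As printed: min(6.5, 8 - w)
- Units aligned: min(6.5, 8 - w/60)

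| w (min) | As printed | Units aligned (h) |
|---|---|---|
| 0 | 6.5 | 6.5 |
| 2 | 6.0 | 6.5 |
| 5 | 3.0 | 6.5 |
| 9 | -1 | 6.5 |
| 45 | -37 | 6.5 |
| 120 | -112 | 6.0 |

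For 45 min: 8 - 45 = -37, against 8 - 45/60 = 7.25, whose minimum with 6.5 is 6.5. On this night the printed form is wrong once w exceeds 8 - 6.5 = 1.5 min. It is negative once minutes awake exceed hours in bed, here above 8 min.

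**2. Mean bedtime.** Take three values, the number used per treatment period: 23:30, 00:30 and 23:45.

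- Plain numbers: (23.5 + 0.5 + 23.75)/3 = 47.75/3 = 15.92 h, or 15:55.
- Hours after noon: (11.5 + 12.5 + 11.75)/3 = 35.75/3 = 11.92 h after noon, or 23:55.

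The error is 8 h. In general, each after-midnight value among three moves the plain mean 24/3 = 8 h earlier, as long as at least one bedtime is before midnight. Bedtimes all before midnight are unaffected: 22:30, 23:00 and 23:30 give 23:00 either way. Get-up times of 06:30, 07:00 and 07:30 give 07:00 either way.

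**3. Time in bed with a bedtime after midnight.** Assume bedtime 00:30 and get-up 07:00 the same morning. The true value is 7.0 - 0.5 = 6.5 h. If 00:30 is given the preceding calendar date, the value is (24 - 0.5) + 7 = 30.5 h, an excess of 24 h. If 00:30 keeps its true date, it no longer belongs to the preceding calendar day, and the rule does not say that it should be used.

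An inflated time in bed does not make adjusted sleep impossible. The minimum simply returns reported sleep, so the intended adjustment is switched off for that night without any sign of it.

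**The case against.** The strongest reply is that every unit is declared. Wake-up time is in minutes and the result is in hours, so a programmer can honour the text only by converting, and would notice a negative sleep time. A reader might infer that the tables will contain impossible values. The documents do not support that: the table shells are separate attachments, and neither they nor the programs are part of the text reviewed. What stands is that the printed formula has to be altered before it can be used.

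Secondly, the SAP nowhere states that bedtimes are averaged as plain numbers across midnight. That is the natural reading of a numeric summary with no reference point, but it is an inference. It is also tempting to extend the problem to get-up times, since they are in the same list. They do not normally straddle midnight, so that extension fails.

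Thirdly, the diary is a daily record, listed in protocol 6.4.5 from get-up time to going-to-bed time. The preceding day can therefore be read as the preceding diary day, which pairs the correct night. That is a fair reading, and the 30.5 h result depends on a dating convention that the documents do not state. The gap in the rule remains.

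Finally, the information on night sleep does not rest on these derived values. Reported sleep and wake-up duration are summarised in the same tables without the formula. All diary data are listed, insomnia is captured through adverse events, and night-time mobility is captured through actigraphy. This limits the consequence and is accepted.

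**Conclusion.** The point holds as a specification error of minor weight. The missing conversion is certain from the text. The bedtime error follows if a numeric summary means a plain mean, and it arises only where bedtimes fall on both sides of midnight, within or across subjects. The 24 h excess in time in bed follows only if a bedtime after midnight is dated to the preceding calendar day.

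In the assumed examples, adjusted sleep is -37 h instead of 6.5 h, mean bedtime is 15:55 instead of 23:55, and time in bed is 30.5 h instead of 6.5 h. How many nights would be affected cannot be judged from the documents.

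A reader might infer that the efficacy conclusions are at risk. They are not. The affected quantities are summarised without a model, a test or a per-protocol table. ESS and the listed secondary endpoints, including sleep attacks and somnolence episodes, do not use them.

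**What to change.** Make three changes to SAP 5.6.8.3:

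1. Write the formula as min(total time slept [h], time in bed [h] - wake-up period duration [min]/60).
2. Summarise going-to-bed time as hours after a fixed anchor such as 12:00 noon. Convert the location statistics back to clock time for display and leave the standard deviation in hours. Get-up time can stay in ordinary clock hours.
3. Compute time in bed from the most recent going-to-bed datetime before get-up, and state that bedtimes after midnight carry their true calendar date even if they were entered on the preceding diary page.

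Then check the programs and shells for Tables 15.3.16.1.S and 15.3.16.2.T against the revised wording, since the conversion may already be coded. The cost is a few lines of SAP text and programming, with no new data. The choice of anchor is a convention: noon is convenient, and any time well away from usual bedtimes would serve.

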## 5.7 Pharmacokinetic Analysis

To assess the steady state pharmacokinetics of the IMP, blood samples will be collected upon subject arrival at study sites during visits VR, V1B, V1C, V2B, V2C, and V3B/EDV. Concentrations of flecainide and modafinil at each visit will be summarised. For summaries, concentrations below the lower limit of quantification (LLOQ) will be set to zero. Concentrations will be reported as collected in listings.

To summarise pharmacokinetic data the geometric mean (GeoMean), geometric standard deviation (GSD), and geometric coefficient of variation (GCV) will be displayed. These statistics will be calculated using the following formulae:

$$GeoMean = \sqrt[n]{y_1 \times y_2 \times \dots \times y_n}$$

$$GSD = e^{(SD(\ln(y_1), \ln(y_2), \dots, \ln(y_n)))}$$

$$GCV = \sqrt{e^{GSD^2} - 1} \times 100\%$$

where  $n$  – number of observations,  $SD$  – standard deviation,  $\ln$  – natural logarithm. Values of ‘0’ will be removed from the calculation of the geometric mean, GSD, and GCV. The ratios GeoMean  $\div$  GSD will be displayed in addition to these statistics.

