8.3.3. Pharmacokinetics

As soon as they are available but only after database has been frozen, analytical determinations will be sent by e-mail (Microsoft Excel® file) by the bioanalytical center of ██████████ to the sponsor's PK expert (with copy to Theranexus, CRO's trial manager). All the transmission of data must be done in blinded condition up to the reception of the certificate of database lock by CRO.

Subsequently, plasma concentrations will be processed for PK data generation.

For the calculation of the PK parameters and characteristics the following rules are usually applied:

- All the plasma concentrations validated by the bioanalytical laboratory and provided to the pharmacokineticist will be used for the PK analysis.
- The actual blood sampling time points related to the preceding administration will be used.
- At time points in the lag-time between time zero and the first concentration equal or above LLOQ (lower limit of quantification), concentrations below LLOQ will be set to zero. Concentrations below LLOQ between two concentrations equal or above LLOQ will be set to half the LLOQ. Trailing concentrations below LLOQ will not be used in calculations.

- For plasma concentration above the upper limit of quantification and reported as ALQ (above limit of quantification) in the final plasma concentration tables, ALQ will be replaced by the first measurement for the PK analysis.
- Not reported concentration will be excluded from the PK analysis.

Plasma concentrations reached at steady state will be presented for modafinil and for flecainide for each visit, considering time after last IMP intake.

Concentration-time data will be listed per treatment and subject for modafinil and for flecainide. Plasma concentrations and time post IMP intake will also be plotted to assess range of exposure at steady state for each treatment and to assess reliability of prediction made by extrapolation from phase I studies for flecainide.

Further details of the pharmacokinetic analyses will be defined in the SAP.

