### 4.1 General Methodology and Presentation of the Results

The default summary statistics for quantitative (continuous) variables will be

- the number of subjects (n),
- mean,
- standard deviation (SD),
- median,
- first quartile (Q1) and third quartile (Q3)
- minimum (min) and maximum (max)

for subjects with data. Additionally, the geometric mean (GeoMean), geometric standard deviation (GSD), and geometric coefficient of variation (GCV) will be displayed for certain variables. Values of '0' will be removed from the calculation of the geometric mean, GSD, and GCV.

Mean, geometric mean, median, and the quartiles will be presented to one more decimal place than the raw value. The minimum and maximum values will be presented with the same decimal precision as the raw value. SD, GSD, and GCV will be reported to two decimal places greater than the original value.

For qualitative (categorical) variables, the frequency count (n) and percentage (%) of subjects with non-missing data per category will be the default frequency tabulations. Where appropriate and present, the number of missing values will be displayed as "Missing" category.

Percentage values are to be presented to one decimal place, for example, 52.3%.

The denominator used for calculation of the percentages will be specified in a footnote to the tables for clarification.

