### Evaluability of pharmacokinetic data

PK samples performed at the end of **treatment periods** will be analysed if an IMP intake was performed in the morning before the PK sample.

PK samples performed at the end of **washout periods** will be analysed if the last IMP intake is 6 or more days before the PK sample, and if the preceding end-of-treatment PK sample is evaluable according to the above rule.

Deviations from these rules will be considered as major protocol deviations in relation to PK analysis.

The following tables and listing will be presented:

Table 15.4.1.S Summary of Pharmacokinetics Concentrations – PK Analysis Set

Table 15.4.2.T Summary of Pharmacokinetics Concentrations – PK Analysis Set

The concentrations of modafinil and flecainide at each visit will be summarised using the geometric mean, geometric standard deviation, and geometric coefficient of variation in addition to the default summary statistics.

Listing 16.2.5.2 Pharmacokinetics Concentrations – Enrolled

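### Concentrations below LLOQ are set to zero and then dropped, so in any mixed cell the PK geometric mean describes only the quantifiable samples and is biased upward

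*SAP*

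**What the plan says.** SAP 5.7 gives the handling rule for summaries: "concentrations below the lower limit of quantification (LLOQ) will be set to zero". Later in the section, and also in SAP 4.1, values of zero "will be removed from the calculation of the geometric mean, GSD, and GCV".

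Blood is drawn "during visits VR, V1B, V1C, V2B, V2C, and V3B/EDV", so the schedule includes the pre-dose baseline and both end-of-washout visits. An end-of-washout sample "will be analysed if the last IMP intake is 6 or more days before the PK sample", provided the preceding end-of-treatment sample is evaluable. SAP 4.6 summarises washout values under the treatment of the period just finished.

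Tables 15.4.1.S and 15.4.2.T show, at each visit, the geometric mean, GSD and "geometric coefficient of variation in addition to the default summary statistics". SAP 4.1 defines the default statistics as n, mean, SD, median, quartiles, minimum and maximum, and gives no zero-removal rule for them. For the raw data: "Concentrations will be reported as collected in listings". The SAP text plans no count of BLQ samples and no separate n for the geometric statistics.

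Protocol 8.3.3 has a different rule for PK parameters. BLQ values in the lag time become zero, trailing BLQ values are not used, and: "Concentrations below LLOQ between two concentrations equal or above LLOQ will be set to half the LLOQ". It leaves further detail to the SAP. SAP section 7 does not list the difference.

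**The concern.** A BLQ result carries information: the concentration was low. Turning it into zero and then discarding zeros treats a low value as if no sample had been taken. What remains is the geometric mean of the samples at or above LLOQ, whatever share of the cell they form.

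Washout cells matter most, because there a reader wants to know whether drug has gone. Two cells with the same quantifiable values, one with 10% and one with 90% of samples BLQ, would print the same geometric mean. Deletion also removes the lower part of the distribution, so GSD and GCV describe only the upper part.

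**Working it through.** The plan gives no PK figure to reproduce, so the check takes the rule, where it bites, and its size.

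**1. The rule.** After BLQ is set to 0 and zeros are removed, GeoMean = exp(mean of ln y over samples with y ≥ LLOQ). Every retained value is at least LLOQ, so the result is too. Any deleted sample lies below every retained one, so a single BLQ sample is enough to put the result above the geometric mean of all samples. If no sample is quantifiable, nothing is left to average and the statistic cannot be calculated.

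**2. Where cells could be mixed.** Inputs are the half-lives of 15 h (modafinil) and 13 h (flecainide) and the modafinil peak of 3.7 to 4.8 µg/mL after 200 mg, from Protocol Table 1. The expected steady-state flecainide peak of about 30 ng/mL at 18 mg/day is from Protocol 1.4.1. The shortest evaluable washout is 6 days = 144 h.

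- Modafinil: 144/15 = 9.6 half-lives; 2^(−9.6) = 0.13% of peak. With accumulation 1/(1 − 2^(−24/15)) = 1.49, the residual is about 7 to 9 ng/mL.
- Flecainide 18 mg: 144/13 = 11.1 half-lives; 0.05% of peak; about 0.014 ng/mL.
- Flecainide 2 mg: peak 30 × 2/18 = 3.3 ng/mL by proportional scaling; residual about 0.0015 ng/mL.
- The protocol calls the flecainide half-life range wide. At an assumed 20 to 27 h, the 18 mg residual at 6 days is 0.2 to 0.7 ng/mL.

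Flecainide washout samples should therefore be mostly BLQ, with some quantifiable in slow eliminators. Modafinil washout depends on the unstated LLOQ. Active end-of-treatment samples require a dose that morning and should be little affected. Flecainide 2 mg is a possible exception if the LLOQ is not far below 3.3 ng/mL.

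**3. Size under a log-normal model.** If a fraction q is BLQ, the printed value divided by the true geometric mean is exp(s × φ(z_q)/(1 − q)), where s is the SD of ln concentration. Both q and s are assumptions.

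| BLQ share q | φ(z_q)/(1 − q) | s = 0.5 | s = 1.0 |
|---|---|---|---|
| 50% | 0.80 | 1.5 | 2.2 |
| 80% | 1.40 | 2.0 | 4.1 |
| 95% | 2.06 | 2.8 | 7.9 |

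**4. Size against LLOQ/2.** Suppose a share p is quantifiable, each at 2 × LLOQ (assumption). The SAP prints 2.00 × LLOQ for every p above zero. Keeping all samples with BLQ = LLOQ/2 gives 2^p × 0.5^(1−p) = 2^(2p−1), in LLOQ units:

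| Quantifiable of 54 | LLOQ/2 rule | SAP rule | Ratio |
|---|---|---|---|
| 5 | 0.57 | 2.00 | 3.5 |
| 10 | 0.65 | 2.00 | 3.1 |
| 27 | 1.00 | 2.00 | 2.0 |
| 45 | 1.59 | 2.00 | 1.3 |

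Only the share matters, not the 54. With 5 or 10 quantifiable, the median with zeros kept is 0.

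**5. Does LLOQ/2 do better?** With few BLQ samples, yes. For a true geometric mean of 2 × LLOQ and log-SD 0.3 to 1.0 (1% to 24% BLQ), the SAP rule gives 1.0 to 1.5 times the truth and LLOQ/2 gives 0.9 to 1.0 times. With a true geometric mean of 0.25 × LLOQ and log-SD 0.7 to 1.0 (92% to 98% BLQ), the SAP rule gives 5.2 to 6.3 times and LLOQ/2 still gives 2.0 to 2.2 times. Substitution does not rescue a mostly-BLQ cell.

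**The case against.** The best defence is that the tables already contain the corrective. The mean, median and quartiles keep the zeros, so a mostly-BLQ washout cell shows a median of 0, and the listings are complete. That stands, and it limits the harm. It does not make the geometric mean beside them correct.

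The table shells are a separate SAP appendix that is not available here. They may already print a BLQ count or a separate n, so the gap can be asserted only for the SAP text.

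Protocol 8.3.3 gives limited support. Its lag-time and between-values logic suits a concentration profile, whereas this trial takes one sample per visit, and it too discards some BLQ values. The point there is only that the SAP differs and does not record it.

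Three stronger readings are tempting, and the documents do not support them:

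- A reader might infer that one mis-dosed subject's sample would become the placebo geometric mean. Protocol 8.3 summarises PK data by the treatment actually received, and the PK analysis set excludes major deviations with an impact on PK. A recognised error would not appear under placebo.
- A reader might infer that the carryover assessment is compromised. SAP 5.6.1 and 5.6.2 assess carryover on ESS, through the treatment-by-period interaction and then first-period and lagged-treatment models. No rule uses washout concentrations.
- A reader might infer that every washout cell will show a positive geometric mean. A cell with all samples BLQ has no calculable geometric mean, and the half-lives make that likely for much of the flecainide washout data.

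**Conclusion.** The point holds as a reporting defect. In any cell that mixes BLQ and quantifiable samples, the planned geometric mean is conditional on quantifiability, cannot go below LLOQ and is biased upward. The direction follows from the two rules alone.

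The size rests on assumptions: about 1.5 to 2.2 times at 50% BLQ and 2.0 to 4.1 times at 80%, for log-normal concentrations with log-SD 0.5 to 1.0. The LLOQ, the BLQ share and the spread are not in the documents. The end-of-washout visits V1C and V2C are the likeliest cells, and flecainide 2 mg at end of treatment is possible.

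PK is a descriptive secondary objective. No efficacy, safety or carryover conclusion depends on these statistics.

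**What to change.** In SAP 5.7 and Tables 15.4.1.S and 15.4.2.T:

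1. Report the number and percentage of BLQ samples in each cell, and the n used for each geometric statistic.
2. Print GeoMean, GSD and GCV as *not calculated* when more than half of the samples in a cell are BLQ, and rely on the median and quartiles there.
3. In cells with a minority BLQ, replace deletion by one stated rule that keeps the samples. LLOQ/2 is a natural choice, because SAP 5.5.2 already sets laboratory range values to half the threshold.
4. Record the difference from Protocol 8.3.3 in SAP section 7.

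The cost is a few sentences and some extra table rows. The downsides are that LLOQ/2 is itself a convention and that some cells will show no geometric mean.

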1.4. Risk/Benefit Ratio

1.4.1. Evaluation of risk

It is anticipated that the safety and tolerance profile of THN102 is similar to that of modafinil given alone in a PD-EDS population, with frequent occurrence of headache, gastric pain, palpitation, tachycardia, dizziness, insomnia, anxiety, confusion, and blurred vision (see Table 1).

For the treatment of tachyarrhythmias, flecainide is given at daily doses between 100 and 300 mg. In the present trial flecainide will be administered for EDS at two very low doses (2 mg, 18 mg as a single daily dose). In previous clinical studies with THN102 flecainide reached a mean (\pm SD) maximal concentration of 44.9 \pm 9.6 ng/mL when 50 mg were given as a single dose (study THN102-101), and of 19.5 ng/mL after 27 mg (3 doses of 9 mg over 20 hours). The C_{max} data appeared linear between flecainide doses of 3, 9, and 27 mg: 2.2 \pm 0.8 ng/mL, 6.4 \pm 2.2 ng/mL, and 19.5 \pm 4.5 ng/mL respectively. Extrapolating from steady state C_{max} of 100 mg of flecainide [25] (173 \pm 46 ng/mL), one would expect a steady state C_{max} for 18 mg/d, the maximal flecainide dose used in this trial, of about 30 ng/mL. This exposure level is well below exposure levels where cardiovascular AEs are expected for flecainide. [27] Flecainide does not trigger any significant cardiovascular effects below 100 ng/mL or even 200 ng/mL in plasma. [28,29,30]

Thus, no cardiac effect is expected at the very low flecainide concentrations associated with the prescribed doses used in this trial and flecainide is not expected to raise any safety and tolerance issue in combination with THN102. As a precautionary measure cardiovascular exclusion criterion 3 has been included.

In the two phase I trials with THN102 the adverse events' profile did not significantly differ between THN102 and modafinil. A small but significant increase in blood pressure and heart rate was noted with both THN102 (400 mg/50 mg) and modafinil (400 mg/0 mg) in trial THN102-101 with 24-hour Holter

monitoring. No impact on cardiac conduction (QT, QRS) and no arrhythmia were seen (for more details, see the IB [31]). The lists of typical adverse events reported for modafinil and for flecainide are also listed in the IB and mentioned in the information for the subject.

Risk will be minimised by regular contact between subject and investigator and by close safety monitoring.

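### The SAP's geometric CV formula uses the already exponentiated GSD, so as written no geometric CV in the PK tables can fall below 131%

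*SAP*

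**What the plan says.** SAP section 5.7 lists three statistics for the plasma concentrations (geometric mean, GSD and geometric CV, abbreviated GCV) and introduces them with "These statistics will be calculated using the following formulae". GSD is the exponential of the standard deviation of the natural logs of the concentrations. The GCV follows directly as "GCV = \sqrt{e^{GSD^2} - 1} \times 100"%. The legend explains only n, SD and ln ("standard deviation, $\ln$ – natural logarithm"). Zeros, which include values below the LLOQ once set to zero, "will be removed from the calculation of the geometric mean, GSD, and GCV".

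The subsection on evaluability of pharmacokinetic data then says that modafinil and flecainide concentrations at each visit "will be summarised using the geometric mean, geometric standard deviation, and geometric coefficient of variation in addition to the default summary statistics". The outputs are Tables 15.4.1.S and 15.4.2.T.

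SAP section 4.1 also names the GCV but gives no formula for it. SAP section 7, on changes from the protocol, does not mention it.

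**The concern.** For log-normal data with log-scale standard deviation s, the geometric CV is sqrt(exp(s²) − 1). Because the SAP defines GSD as exp(s), the quantity to be squared in the exponent is ln(GSD). The SAP squares GSD itself.

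The GSD can never be less than 1, so the exponent can never be less than 1 and the result has a floor well above zero. A variability measure that cannot be near zero when the data do not vary is not measuring variability on the intended scale.

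Steady-state plasma levels of both drugs are a secondary objective (Protocol 2.2, SAP 2.1.2). Protocol 8.3.3 wants the range of exposure described and the flecainide predictions extrapolated from phase I checked. A geometric CV several times too large would mislead anyone who uses it for either purpose. It would also clash with the arithmetic mean and SD printed in the same table. The SAP gives SAS code for the efficacy models but none for the PK summaries, so the printed formula is the only specification for this statistic in the SAP text.

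**Working it through.** The documents state no numerical geometric CV, so there is no figure to reproduce. The check evaluates the two formulae side by side.

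**Inputs**
- GSD = exp(s), with s = SD(ln y) (SAP 5.7).
- SAP formula: GCV = sqrt(exp(GSD²) − 1) × 100%.
- Log-normal formula: GCV = sqrt(exp(s²) − 1) × 100%, with s = ln(GSD).
- Zeros are dropped, so ln y exists for every value used, and s ≥ 0.

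**Floor.** If all concentrations are equal, s = 0 and GSD = 1.
- SAP: sqrt(e¹ − 1) = sqrt(1.71828) = 1.3108, or 131.1%.
- Log-normal: sqrt(e⁰ − 1) = 0%.

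Since s ≥ 0 implies GSD ≥ 1, and the SAP expression increases with GSD, 131.1% is its minimum.

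**Can the two formulae ever agree?** They agree only if GSD² = s², that is e^(2s) = s². Because e^s > s for every s ≥ 0, e^(2s) is always larger than s². The SAP value therefore exceeds the correct one at every spread. A grid over 0 ≤ s ≤ 3 puts the minimum of e^(2s) − s² at 1, reached at s = 0.

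**One value in full, s = 0.3**
- GSD = e^0.3 = 1.3499, and GSD² = 1.8221.
- SAP: exp(1.8221) − 1 = 5.185; the square root is 2.277, or 227.7%.
- Log-normal: exp(0.09) − 1 = 0.09417; the square root is 0.3069, or 30.7%.

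**Other values**

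| s = SD(ln y) | GSD | Correct GCV | SAP formula |
|---|---|---|---|
| 0 | 1.000 | 0% | 131.1% |
| 0.1 | 1.105 | 10.0% | 154.7% |
| 0.2 | 1.221 | 20.2% | 185.6% |
| 0.3 | 1.350 | 30.7% | 227.7% |
| 0.5 | 1.649 | 53.3% | 376.2% |
| 1.0 | 2.718 | 131.1% | 4,021% |

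**Illustration from the protocol's own figures.** Protocol 1.4.1 gives flecainide Cmax as mean ± SD for four doses in the THN102 phase I trials, for example "44.9 \pm 9.6 ng/mL when 50 mg were given as a single dose". Assuming log-normality, an arithmetic CV converts to s = sqrt(ln(1 + CV²)). For 50 mg, CV = 9.6/44.9 = 0.2138, so s = sqrt(ln(1.0457)) = 0.2114 and GSD = 1.2354.

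| Flecainide dose | Mean ± SD (ng/mL) | s | Correct GCV | SAP formula |
|---|---|---|---|---|
| 50 mg | 44.9 ± 9.6 | 0.2114 | 21.4% | 189.8% |
| 27 mg | 19.5 ± 4.5 | 0.2278 | 23.1% | 196.0% |
| 9 mg | 6.4 ± 2.2 | 0.3342 | 34.4% | 245.7% |
| 3 mg | 2.2 ± 0.8 | 0.3524 | 36.4% | 256.2% |

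Spreads of 21% to 36% would be printed as 190% to 256%.

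**The case against.** The algebra is not in dispute. The case on the other side concerns certainty and consequence.

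- **The program has not been seen.** The table shells are separate files (SAP section 9) and the code is not in the documents. If the programmer used the log-scale SD, the printed values will be right. This stands, and it makes the effect on the output conditional. It does not clear the SAP: correct code would then be an undocumented departure from the plan.
- **Little hangs on the statistic.** The same tables show the geometric mean, the GSD, and the default mean, SD, median, quartiles and range, all of which are unaffected. A reader could recover the right value from the printed GSD. No test, threshold or decision uses the GCV. This also stands, and it lowers the seriousness of the error.
- **The Cmax example is not a forecast.** It comes from healthy volunteers after a single dose or three doses within a day. This trial takes one sample on arrival at the site (Protocol 6.5), in patients aged up to 80. The example assumes log-normality and gives nothing for modafinil. It shows the size of the distortion at a plausible spread and should be read only that way. The floor and the s-based table do not depend on it.

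A PDF-reading fault is unlikely: both formula lines are complete, and the GCV line uses the symbol defined just above it.

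**Conclusion.** The formula is wrong as written. It inflates the geometric CV at every possible spread and cannot return less than 131.1%. For log-scale SDs of 0.1 to 0.5, values that should read 10% to 53% would read 155% to 376%.

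That every reported GCV will be wrong rests on one assumption, that the program follows the printed line. The comparison values rest on the usual log-normal definition of the geometric CV.

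The effect is confined to the GCV entries of the two PK concentration tables. The error is definite but of moderate weight: it bears on how a secondary objective is described, not on any inference from the trial.

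**What to change.** In SAP 5.7, replace the GCV line with

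GCV = sqrt(exp((ln GSD)²) − 1) × 100%,

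or equivalently sqrt(exp(s²) − 1) × 100% with s = SD(ln y). Leave the GSD definition as it is.

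Then check the program for Tables 15.4.1.S and 15.4.2.T, and any shell footnote that repeats the formula. A quick test is to feed in concentrations that are all equal: the output should be 0%, not 131%. If the code already uses the log-scale SD, only the SAP text needs correcting, and the correction should be recorded.

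The cost is one line in the SAP and, if the printed formula was programmed, one line of code. No data, design or blinding is touched.
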